### **Specific issues and approaches for the analyses of the Specific Aims.**

**Aim 1: Evaluate the efficacy of PN intervention.** The primary focus of the analyses will document differences on our primary outcomes (alcohol use and alcohol-related harms) and secondary outcomes (marijuana use, nicotine use, and their combined use with alcohol) between the groups (PN/Control) using a mixed measures analysis of variance. A 2 X 3 (groups X time) MANCOVA will test the impact of the PN intervention on our outcome variables contrasting baseline tendencies against follow-up assessments (3 waves: baseline, 1 mo., and 6 mo.). For Aim 1 (analysis of efficacy), we will conduct an intent-to-treat analysis that will include all individuals who have been randomized to a condition. We will also examine differences in all outcomes by sex of the student (as a relevant biological variable), sexual orientation, and gender identity adding these as covariates to the analyses. We will be sensitive to inflated experiment-wise error rates and control these with modified Bonferroni methods.

**Aim 2: Examine mediators.** The second aim examines mediation paths in Figure 1 using SEM. We will follow the recommendations of MacKinnon (joint significance). For example, we will examine the relationship between the effects of the PN on predictors at the immediate post-PN assessment (1 mo. follow-up) and their subsequent effects on outcomes at the 6 month follow-up. The models will be statistically over-identified. We will examine global fit indices and focused indices of fit diagnostic of specific points of ill fit in the model (e.g., standardized residuals for predicted minus observed variances and covariances, and modification indices). We will use robust standard errors and bootstrapping. In the face of poor model fit, we will examine diagnostics that are conceptually meaningful and will significantly improve model fit.

[figure not shown]
A more sophisticated analysis of efficacy focuses on “growth trajectories” and how these vary by intervention groups. In general, there are two analytic approaches to growth curves, one based on SEM and the other based on the framework of Hierarchical Linear Modeling. We will use the SEM framework to illustrate the basic logic using developmental changes in student alcohol use as an example. This same approach will be used to examine other outcomes. Figure 2 presents a simplified path model illustrating the logic of the approach. In Figure 2, alcohol use is represented by a latent construct at each time point (“T” in the design (T1, T2, T3)). We initially discuss the approach assuming a linear trajectory over time, but consider non-linear trajectories shortly. For the variable of interest, a latent intercept variable and a latent slope variable are parameterized, with latent variances of those variables reflecting individual differences in the line that describes growth (either the slope or the intercept) and latent means reflecting the average intercept and slopes, respectively. Paths from the latent variables to the observed measures are fixed at strategically-selected

constants so that the latent intercept reflects the observed measure at baseline and the latent slope reflects the slope of the line describing the trajectory. Individual differences in the slope can be modeled by including time-invariant variables in the model with causal arrows extending to the latent slope variable. This is illustrated in Figure 2 by PN/Control, sex, and the interaction of the two. The statistical machinery for this is well developed and described. We will be sensitive to testing, where possible, matters of metric equivalence across time (in the form of equal factor loadings over time see 88). We expect to observe metric equivalence but will be sensitive to the need to test this assumption. We suspect that some of the trajectories will be non-linear. One strategy for modeling non-linear trajectories is to use polynomial regression methods that define latent linear quadratic variables, but this often yields difficult to interpret parameter estimates. Our preference is to use spline regression where spline knots are identified and slopes are evaluated between knots. This is incorporated into growth curves and involves representing slopes defined by knots as a latent variable.

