KB will refine and complete the digital programming of PN in consultation with the research team. Investigators have developed goals and specific instructional/behavioral objectives and content for the PN in Phase I. During Phase II, KB will iteratively share content with all members of the team who will review and provide feedback for any remaining revisions. We used a combination of emails, telecommunications, Zoom teleconferencing, and in-person meetings in Phase I (meeting weekly and more often as needed). We will utilize this same approach in Phase II. This process will continue until all necessary improvements are made. Following completion of the digital programming for the remaining modules, we will conduct a usability study that mirrors the approach we used in Phase 1. The functionality of the PN program will be tested by KB on a small group of parents (~n = 5-7). Edits will be made based on these findings and then tested again on another small group of parents (~n = 5-7). Based on our experience on the development time in Phase I, we anticipate this process to be completed in 6 months.

**Limitations and Alternative Methods for Objective 1.** Face-to-face delivery and/or a longer curriculum may be more effective in reducing substance use. Future research should compare modalities, but the current design facilitates delivery with minimal training and increased consistency, maximizing usability with varied groups. A native mobile app could be produced but it is more expensive and can take longer to produce for multiple device operating systems, is more challenging to update, and its use cannot be as easily monitored as a web app.

**Milestones/Deliverables for Objective 1.** The benchmark for Objective 1 is when all of the above steps are accomplished and PN is revised to specifications and fully operational with a high degree of usability as expressed in SUS scores above the 68 standard.

**Objective 2: Conduct a randomized clinical trial to evaluate outcomes of the PN curriculum. Randomized Trial Design.** The design is a two-arm RCT (PN vs. active control) with 3 waves of data collection: pre-intervention baseline, short-term follow-up (1-month), and longer-term follow-up (6-month). The study will enroll a nationally representative sample of 400 parent-student dyads through GfK Custom Research (formerly known as Knowledge Networks). Youth will complete assessments of all the variables in

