As noted above, teens who complete their consent will be routed to an online survey. After the baseline assessment, parents will be randomized equally to 1 of 2 groups. Parents in the treatment condition will receive a link to KB’s secure server to access PN and complete a brief question set assessing their parent communication style. Parents in the control condition will receive a link to that server to access publicly available SAMHSA alcohol prevention materials for parents. Both conditions take the same length of time to navigate. Parents in both conditions will be instructed to access the materials and discuss the information with their teens during the next month. Thus, the proposed research will have a strong active control condition for which to examine differences in effects increasing the rigor of the study. The link to the website will contain instructions on how to register and use the site. Parents who do not register with the website will receive reminders every 5 days for three weeks; after three weeks, study staff will contact parents by telephone and encourage them to register. RP staff will provide technical assistance if parents have problems using the website. In our previous studies, we have had parental compliance rates with web surveys, parenting materials

from the Parent Handbook, parent-ratings of the Parent Handbook and so on, that have reliably exceeded 88%. We anticipate no problems regarding use of the PN in the proposed research.

Teen participants in both the treatment and control groups will receive a follow-up survey (~15 minutes to complete) at 1 and 6 months post-baseline, which will allow us to examine any changes in the proposed mediator variables. Parents randomized to the PN condition will complete a brief question set at the beginning of the PN intervention that assesses parenting communication style and allows for personalization. Parents also receive an immediate posttest to measure fidelity and reactions to PN. Baseline, 1- and 6-month follow-up surveys will each take approximately 25-30 minutes to complete.

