**Participant retention and plans to increase retention.** Our retention goals are to have a final sample representative of the U.S. population, free of sample bias, and of sufficient power to address our study aims (see Attrition and Statistical Power sections below). This has been our experience in two large-scale national sample studies with GfK. As indicated, GfK's panels tend to outperform other large national panels on known and standard benchmarks (e.g., Census data). GfK's panels typically observe a 2% monthly panel attrition rate that is not-study specific, study-specific retention rates of 80% for short-term follow-ups (1-3 months) and 70% retention in longer-term follow-ups (6-12 months). In [name]'s recent national RCT study with GfK, he observed a 78% participation rate for teens similar to the proposed study and retained 88% at 12 months. Our procedures make every attempt to reduce attrition by keeping respondent contact information current and using methods we have employed in our past work. First, in the initial baseline survey, participants will list and provide contact information for two individuals they DO NOT live with whom we may contact in the event we are unable to locate participants with our contact information, as well as a cell phone number at which they can receive text message reminders. Second, at the beginning of each post-assessment, participants will be contacted by email and asked to update their own contact information and that of the two individuals they indicated as contact individuals in the previous assessment. If they do not respond, we will follow-up by phone. Finally, we will provide sufficient incentives and multiple contacts (up to 7 email reminders) that help with high retention. Using these procedures for the 400 parent-student dyads at baseline, we anticipate the 2% monthly non-study specific attrition will result in n's of 320 and 280 dyads at the 1- and 6-month follow-ups.

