## Recruitment and Retention Plan

### Recruitment

The sample will be recruited in Year 1. Parent-teen dyads will be invited to participate and complete baseline assessment during the fall semester and parents will receive the Parenting Now or active control materials shortly afterwards. This will allow an examination of the impact of the PN on alcohol use, and associated consequences and sustained effects across the 6-month follow-up period.

We will use GfK Custom Research (formerly known as Knowledge Networks)'s tested and nationally vetted procedures that have consistently resulted in nationally representative samples free of sample bias. GfK panels use dual frame recruiting (address-based and random digit dialing; RDD) and statistical sampling to select potential panel members from the general U.S. population. All U.S. households and the members within have a known, calculated probability for being selected to join GfK panels. Using known probability information ensures that GfK panel samples are statistically representative across the multiple socio-demographic population characteristics published and updated monthly by the U.S. Census Bureau. Thus, GfK panels use the same principles used in high-quality RDD telephone surveys. Therefore, GfK recruitment and survey collection procedures are able to minimize 1) coverage bias, and 2) self-selection bias through use of random sampling techniques. In addition, GfK panels report an excellent record of reducing non-response bias in its panels, with response averages ranging from 50-90% (compare this to 25-50% reported response averages for RDD surveys).

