4.3. Outcome Measures

Type	Name	Time Frame	Brief Description
Primary	Alcohol Use	Project years 1-2	A standard drink definition will be provided: a standard drink consists of 12 oz. beer or wine cooler, 8.5 oz. of malt liquor, 4 oz. of wine, 3.5 oz. fortified wine, or 1.5 oz. of hard liquor. Typical weekly drinking: participants will respond to the Daily Drinking Questionnaire(DDQ; Collins et al., 1985) to indicate number of drinks consumed on each day of a typical week within the past six months. Participants will report maximum number of drinks consumed on an occasion within the past month and number of hours spent drinking on that occasion using the Quantity/Frequency/Peak questionnaire (QFP; Dimeff et al., 1999; Marlatt et al., 1998). Drunkenness will be assessed by asking how many times in the past month participants have gotten drunk, or very high from alcohol using a 6-point scale: (0) never to (5) 9 or more. Heavy episodic drinking will be measured for females and males separately, asking for number of times they've had 4/5, respectively, drinks in a row within two hours.
Secondary	Marijuana Use	Project years 1-2	Frequency of use will be assessed by asking how often participants used marijuana during the past six months using a 7-point scale ranging from (0) never to (6) 40 or more times.
Secondary	Combined Use	Project years 1-2	Frequency of combined use will be assessed for participants indicating marijuana and nicotine use with a single item: During times you used marijuana, how often did you also drink alcohol? using a 6-point scale ranging from (0) never to (5) 40 or more times. For participants that indicate their peak drinking occasion a follow up question will assess whether marijuana or nicotine was also used(yes or no).
Secondary	Consequences of Alcohol Use	Project years 1-3	Alcohol-related consequences (e.g., said or done embarrassing things, blackout) from the past six months will be measured using the established Brief Young Adult Alcohol Consequences Questionnaire (BYAACQ; Read, Kahler, Strong, & Colder, 2006). Response options will again be measured on the same a 7-point scale above.
Secondary	Nicotine Use	Project years 1-2	Frequency of use will be assessed by asking how often participants used nicotine products (tobacco, vaping, snuff) during the past six months using a 7-point scale ranging from (0) never to (6) 40 or more times.

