## Statistical Design and Power

**Design:** The design is a two-arm randomized control trial with 3 waves of data collection (PN vs. Control). The study will enroll a nationally representative sample of 400 parent-student dyads through GfK Custom Research (formerly known as Knowledge Networks). All dyads will complete assessments of the variables in Figure 1 at three times: pre-intervention baseline, immediate follow-up (1-mo.), and a short-term follow-up (6-mo.).

**Power:** The sample sizes were chosen based on statistical analytic and theoretical considerations. For Aim 1—examining the efficacy of the PN, we will have final dyad sample  $n = 400$ . This translates into our two groups (PN/Control) each having  $n$ 's of  $\sim 200$  at the 1- and 6-month follow-ups. Using power estimation procedures described in Cohen, these sample sizes will yield power of greater than 0.80 for small effect sizes (e.g., 5–10% of the outcome variance) in the MANCOVA-based analyses (omnibus tests, interactions, and planned comparisons). In our published papers with similar  $N$ s comparing drinking or marijuana (primary outcomes) for similar parenting-based interventions and controls, we have detected effect sizes of .05 to .09 for main effects and .05 to .08 for interactions. We will have similar power for comparing consequences of alcohol (secondary outcomes). Thus, with our final  $N$ s we should have sufficient power to evaluate Aim 1.

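### No section names the follow-up wave that decides H1, and the stated group-by-time test does not by itself separate an effect gone by 6 months from a sustained one

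*Combined protocol and SAP*

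**What the plan says.** - **Design** (Approach, Objective 2): "The design is a two-arm RCT (PN vs. active control) with 3 waves of data collection", namely baseline, 1 month and 6 months. Allocation is 1:1 ("After the baseline assessment, parents will be randomized equally to 1 of 2 groups").
- **H1** (Significance, Aim 1): less alcohol use and fewer consequences under Parenting Now (PN) than under control. No time point is given.
- **Aim 1 analysis** (Data Analysis): "A 2 X 3 (groups X time) MANCOVA will test the impact of the PN intervention on our outcome variables". Baseline is contrasted with the follow-ups, without saying whether that means 1 month, 6 months or both.
- **Other efficacy analyses:** Statistical Design and Power mentions planned comparisons within the MANCOVA but lists none. The growth-trajectory text that follows Aim 2 prefers spline slopes between knots, without placing the knots or naming a decisive slope.
- **Success benchmark** (Indicators of Success/Benchmarks): the item ranked most important is an effect on behavior, with no wave attached. The item before it, on mediators, does name 1 month.
- **Objective** (Recruitment and Retention Plan, repeated in Protection of Human Subjects): to examine the impact of PN and "sustained effects across the 6-month follow-up period".
- **Outcome table** (4.3): the time frame is "Project years 1-2" for alcohol use and "Project years 1-3" for consequences. Neither is an assessment wave.
- **Retention** (Participant retention): attrition "will result in n's of 320 and 280 dyads at the 1- and 6-month follow-ups".

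**The concern.** H1 is directional: PN teens should drink less. A 2 x 3 group-by-time interaction asks something broader, namely whether the arms' profiles over three waves differ in any way. A benefit at 1 month that has disappeared by 6 months satisfies it, and so does a benefit that turns into harm. A significant result therefore does not show that the stated objective of a lasting effect has been met.

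Because no wave is named, an analyst with a significant interaction could report whichever follow-up looks better as the finding on H1. Dissemination depends on the evaluation being successful (Specific Aims), so this choice bears on the trial's main practical decision.

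**Working it through.** **1. The plan's own power figure.** Statistical Design and Power claims power above 0.80 for 5–10% of outcome variance with about 200 per arm. At 5%, f² = 0.05/0.95 = 0.0526. With N = 400, λ = 0.0526 × 400 = 21.05, and power at alpha 0.05 is above 0.99 (1 df) or 0.99 (2 df). With the 280 dyads projected at 6 months, λ = 14.74 and power is 0.97 or 0.94. The claim reproduces as an inequality, so the point here is not a shortage of power.

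**2. Inputs for the comparison of patterns.**
- From the plan: two equal arms; 280 dyads at 6 months, so 280/2 = 140 per arm.
- Assumed, because the plan gives no value: alpha 0.05, a 0.3 SD difference, and the correlations between waves.
- Simplifications: one outcome at a time, complete data at all waves, normal approximation.

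**3. Equal correlation r between waves.** Let d = (difference at 1 month, difference at 6 months), each as change from baseline in SD units. The covariance of the two estimated differences is V = (2/n)(1−r)[[2, 1], [1, 2]]. The 2-df test has noncentrality d′V⁻¹d = (n/2) × (2/3)(d₁² − d₁d₂ + d₂²)/(1−r).

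With n = 140 and r = 0.5:

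| Pattern | d | Noncentrality | Rejection, 2-df test |
|---|---|---|---|
| Gone by 6 months | (0.3, 0) | 70 × (2/3) × 0.09/0.5 = 8.4 | 0.74 |
| Sustained | (0.3, 0.3) | 8.4 | 0.74 |
| Delayed | (0, 0.3) | 8.4 | 0.74 |
| Benefit, then equal harm | (0.3, −0.3) | 70 × (2/3) × 0.27/0.5 = 25.2 | above 0.99 |

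At r = 0.7 the first two noncentralities are 14.0 and both rejection rates are 0.93.

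**4. Correlation that decays with time, AR(1) 0.6** (0.6 between adjacent waves, 0.36 between baseline and 6 months). Per person, the variances of the two changes are 2(1−0.6) = 0.80 and 2(1−0.36) = 1.28. Their covariance is 1 − 0.6 − 0.36 + 0.6 = 0.64, and the determinant is 0.80 × 1.28 − 0.64² = 0.6144.
- Gone by 6 months: 70 × 0.09 × 1.28/0.6144 = 13.1, rejection 0.91.
- Sustained: 70 × 0.09 × (1.28 + 0.80 − 2 × 0.64)/0.6144 = 8.2, rejection 0.73.

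**5. A single 6-month contrast** (n = 140, r = 0.5).
- Vanished effect: rejects 5% of the time, by construction.
- Sustained 0.3 SD, as a change score: z = 0.3/√(2 × 1.0/140) = 2.51, power 0.71.
- Sustained 0.3 SD, adjusted for baseline: residual variance 1 − 0.5² = 0.75, z = 0.3/√(2 × 0.75/140) = 2.90, power 0.83.

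**6. Which wave the documents favor.** Section 4.3 asks about typical weekly drinking and consequences over the past six months. Participant Recruitment and Procedures places the first follow-up 1 month after baseline, so about 6 − 1 = 5 of the 6 recalled months precede the intervention. Peak drinking and drunkenness use a past-month window and do not have this problem. The Aim 2 analysis already uses 1 month for mediators and 6 months for outcomes.

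**The case against.** **The trial can study persistence.** A reader might infer that the sustained-effects objective cannot be answered. The documents do not support that. Teen outcomes are collected at 6 months, planned comparisons are foreseen, and spline growth models by arm could show fade-out after 1 month. This stands. What is missing is a decision about which of these counts.

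**The equality is not a general property.** A reader might also infer that the test always rejects equally often for both patterns. That is exact only when the 6-month value correlates equally with baseline and with 1 month, and the plan states no correlations. This stands too, although under decaying correlation the vanished effect is favored.

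**The calculation is not the plan's analysis.** A MANCOVA taking several outcomes jointly has more than 2 df. The plan intends intent-to-treat with imputation or full-information likelihood, not 140 complete cases per arm. The 0.3 SD is not in the documents either: 5% of variance corresponds to d = 2√0.0526 = 0.46. All true, so the rates are illustrations. At 0.46 SD (n = 140, r = 0.5), however, the 2-df test rejects 0.98 for the vanished and the sustained effect alike, so a larger effect does not remove the ambiguity.

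**Six months is a choice.** H1 does not promise it, retention is lower there, and a 6-month contrast alone cannot separate a sustained from a delayed effect. The last is correct, but both leave a benefit at 6 months, and a secondary 1-month contrast tells them apart.

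**Success also requires the conceptual model to hold**, illustrated with 6-month outcomes. That makes a claim resting on 1 month alone less likely, but it does not fix the wave for H1.

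**Conclusion.** The concern holds in limited form. No section names the wave that decides H1, and a significant 2 x 3 interaction is not evidence that an effect lasts to 6 months. Under the stated assumptions the test rejects 0.74 for both patterns at equal correlation 0.5, and 0.91 (vanished) against 0.73 (sustained) under AR(1) 0.6. A baseline-adjusted 6-month contrast separates them: 5% against 0.83 at correlation 0.5. These rates depend on the assumed effect, correlations and complete-case numbers; the lack of a named wave does not.

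The risk is that the deciding wave could be chosen after the data are seen, not that it will be. The time frames in 4.3 and the two-year participation entry in 4.5 are clerical: the waves are clear elsewhere, and these entries add no weight to the point.

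**What to change.** - **H1 and the Aim 1 analysis:** pre-specify the baseline-adjusted PN-minus-control difference in the primary alcohol outcome at 6 months as the contrast that decides H1.
- **1-month contrast:** make it secondary, for short-term effect and mediator timing.
- **Omnibus group-by-time test and growth models:** label them supportive.
- **Clerical:** in 4.3 replace the project-year time frames with the actual waves, and in 4.5 give the actual baseline-to-6-month duration.

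This changes wording only, with no new visits or data. There are two costs. A benefit seen only at 1 month could not be claimed as success on H1, and the decision would rest on the wave with lower projected retention, 280 rather than 320 dyads.

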**Randomization.** GfK starts with estimates for survey completion rate, incidence (confirmation of teen’s age and consent), and the number of subgroups. These estimates are used to determine the estimated number of eligible parents who have children of study age. GfK then selects the sample of parents from their panels. Parents are then screened for eligibility and consented. Parents that provide consent are assigned numbers based on a random number table sequence and then randomly assigned to one of the study arms.

**Data Collection and Measurement.** As noted above, self-report surveys programmed and facilitated by GfK will be completed online, at up to 3 timepoints: baseline and 1- and 6-months post intervention (Table 2). In addition, program analytics will be examined to help ensure fidelity to the intervention, and to be included as covariates in all analyses.

**Self-Report.** Table 2 describes the self-report measures to be assessed, consistent with our conceptual model depicted in Figure 1, including primary, secondary, and tertiary outcomes. As indicated above, both teens and parents will complete online surveys through GfK. This self-report methodology is consistent with major national epidemiological surveys of teen substance use, as well as [name]’s prior work in this area, and is demonstrated to be valid. Participants will be made aware of the importance of the data, the confidential nature of their responses, and that the research team will follow appropriate procedures to secure their privacy.

PN Program Analytics. Program analytics (i.e., log data) to be collected include total time spent accessing PN, time spent on each module and activities within modules, and number of activities and modules completed. These data will be captured through HTML5 programming and downloaded into Excel. From this data, we will be able to examine the depth of parents’ immersion in the program and distinguish between users who quickly moved through the program versus those with a deeper level of engagement as well as assess accuracy and use them to assess effects of program exposure (i.e., dose).

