**Table 2. Measures Reflective of Theoretical Model in Figure 1**

Construct	Target	Time	alpha
Primary Outcomes			
Alcohol Use (Daily Drinking, HED, Quantity/Frequency, Peak) 	Teen	T1-T3	>.70-.90
Alcohol-related Consequences (e.g., Riding with a drunk driver) 	Teen	T1-T3	>.75-.85
Secondary Outcomes			
Marijuana Use 	Teen	T1-T3	>.70-.90
Nicotine Use (e.g., Cigarette Use; E-cigarette Use; Smokeless Tobacco) 	Teen	T1-T3	>.70-.90
Combined Substance Use	Teen	T1-T3	>.70
Tertiary Outcomes (Mediators)			
Parent Communication 	Parent,Teen	T2	>.75
Alcohol Motives/Expectancies/Willingness/Norms 	Teen	T2	>.70 - >.85
Moderators			
Background Demographics (Birth Sex, Gender Identity, Sexual Orientation, Age, Race / Ethnicity)	Teen	T1	–

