**Measurement Error.** Where possible, we will adopt strategies that explicitly model measurement error (e.g., use multiple indicators in SEM). For single indicator models, measurement error can be modeled by fixing error variances of measures at a priori specified values that map onto the reliability of these measures suggested by previous research. If it is a multi-item measure, we can create multiple indicators using split-half methods. In cases where we cannot formally model measurement error influences, we will take care to recognize biasing effects of measurement error when interpreting the results of statistical analyses.

**Covariates.** In our modeling efforts, there may be confounds with some of our core explanatory variables. These confounds will be addressed by statistically controlling for them as covariates in our estimating equations. The choice of covariates is non-trivial, and one must be careful not to engage in atheoretical

partialling. Our approach will be to control if: (1) it is thought to be a source of spuriousness, and/or (2) it is correlated with the key variable(s) in the model but is thought to have an independent effect on the criterion. We will carefully consider the role of variables and explore models as is theoretically appropriate.

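### The Aim 1 group-by-time MANCOVA uses baseline as a level of the outcome and names no baseline covariate, so it gives up precision that the data already collected could supply

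*Combined protocol and SAP*

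**What the plan says.** The Aim 1 paragraph under the specific issues and approaches for the analyses states that a 2 × 3 group-by-time MANCOVA "will test the impact of the PN intervention on our outcome variables contrasting baseline tendencies against follow-up assessments". The same sentence places baseline inside the repeated factor, "contrasting baseline tendencies against follow-up assessments (3 waves: baseline, 1 mo., and 6 mo".

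The covariates named elsewhere are:

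- Aim 1 paragraph: sex of the student, "sexual orientation, and gender identity adding these as covariates to the analyses".
- Data Collection and Measurement: program analytics, "to be included as covariates in all analyses".
- Randomization Bias: demographic and background variables, if the arms differ on them.
- Covariates (general rule): a variable may be controlled if "it is correlated with the key variable(s) in the model but is thought to have an independent effect on the criterion". This would admit the baseline outcome but does not commit to it.

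The baseline value of the outcome is named in none of these. It is collected: Table 2 lists the primary outcomes, beginning "Alcohol Use (Daily Drinking, HED, Quantity/Frequency, Peak", at all three waves. Under Participant Recruitment and Procedures, parents are randomized 1:1 after the baseline assessment. The section on intervention materials and follow-up surveys agrees. On retention, the plan expects that attrition "will result in n's of 320 and 280 dyads at the 1- and 6-month follow-ups".

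**The concern.** When baseline is a level of time, the treatment effect sits in the group-by-time interaction: the difference between arms in change from baseline. That contrast subtracts the whole baseline value. If baseline predicts follow-up imperfectly, this subtracts too much and adds baseline noise to the estimate. Regression on baseline subtracts only the predictable part.

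In a randomized comparison with baseline measured before allocation, the true baseline means are equal. The usual reason to prefer change scores, pre-existing group differences, is therefore absent. Both estimators target the same effect without bias, and only their precision differs. At stake is avoidable loss of efficiency in the main efficacy test, in a trial that expects 280 of 400 dyads at 6 months.

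**Working it through.** **Inputs from the documents.** 400 dyads, 1:1; 320 expected at 1 month and 280 at 6 months; planned effect 5% to 10% of outcome variance; stated power above 0.80 (Statistical Design and Power).

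**Not in the documents, so assumed.** Baseline to follow-up correlation ρ (Table 2 gives only reliability alphas); ratio k of follow-up SD to baseline SD; alpha 0.05 two-sided. The 5% is read as a share of raw follow-up variance.

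**Step 1. The plan's own power figure.** For R² = 0.05, f² = 0.05/0.95 = 0.0526 and d = 2√0.0526 = 0.459. Noncentral F power is 0.996 (1 df) or 0.989 (2 df) at N = 400, and 0.969 or 0.938 at N = 280. The claim of more than 0.80 is reproduced at both sample sizes.

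**Step 2. Direction.** Set the baseline SD to 1. Per-person variance is:

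- change contrast: k² + 1 − 2kρ
- baseline-adjusted: k²(1 − ρ²)

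The difference is (1 − kρ)², which is never negative and is zero only when kρ = 1. So adjustment is at least as precise for any correlation and any SD ratio, apart from the degree of freedom spent on the slope.

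**Step 3. Size, equal SDs (k = 1), one follow-up.** The variances become 2(1 − ρ) and 1 − ρ². Their ratio is (1 + ρ)/2, so the reduction is (1 − ρ)/2. The detectable effect at 80% power is 2.80 × √(4/280 × variance factor).

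| ρ | Variance cut | SE cut | 280 adjusted act like | Detectable effect, change | Detectable effect, adjusted |
|---|---|---|---|---|---|
| 0.4 | 30% | 16% | 400 | 0.37 SD | 0.31 SD |
| 0.5 | 25% | 13% | 373 | 0.33 SD | 0.29 SD |
| 0.6 | 20% | 11% | 350 | 0.30 SD | 0.27 SD |
| 0.7 | 15% | 8% | 329 | 0.26 SD | 0.24 SD |

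A simulation with 140 per arm and 4,000 runs gave variance cuts of 29% at ρ = 0.4 and 15% at ρ = 0.7.

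**Step 4. Sensitivity.** The cut is (1 − kρ)²/(k² + 1 − 2kρ).

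- k = 0.8: 0.4624/1.00 = 46% at ρ = 0.4; 0.1936/0.52 = 37% at ρ = 0.7.
- k = 1.2: 0.2704/1.48 = 18% at ρ = 0.4; 0.0256/0.76 = 3% at ρ = 0.7.
- Mean of both follow-ups against baseline, k = 1, all correlations equal: 1.5(1 − ρ) against (1 + ρ)/2 − ρ². That is 0.90 against 0.54 at ρ = 0.4 (40%), and 0.45 against 0.36 at ρ = 0.7 (20%).

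**Step 5. Consequence for power** (280 completers, k = 1, one follow-up; change contrast, then adjusted).

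| Effect | Alpha | ρ = 0.4 | ρ = 0.7 |
|---|---|---|---|
| d = 0.459 (planned minimum) | 0.05 | 0.94, 0.99 | 0.999, 1.000 |
| d = 0.30 (assumed smaller) | 0.05 | 0.63, 0.78 | 0.90, 0.94 |
| d = 0.459 | 0.01 | 0.82, 0.95 | 0.99, 1.00 |
| d = 0.30 | 0.01 | 0.39, 0.56 | 0.75, 0.83 |

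Alpha 0.01 illustrates the strictest step (0.05/5) of a modified Bonferroni procedure over the four alcohol-use measures and consequences that Table 2 lists as primary.

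**The case against.** **The plan has other routes to baseline adjustment.** The general covariate rule would admit the baseline outcome. The latent growth model, described after the Aim 2 text, carries baseline in the intercept and shows group acting on the slope. If group has no path to the intercept, baseline means are held equal and the precision can be recovered. Both points are fair. But the rule commits to nothing, and the growth model is offered to illustrate the logic and is not designated as the main test. Figure 2, which might settle its paths, is not available. Neither changes the MANCOVA that the Aim 1 paragraph specifies.

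**The loss may be small.** Alcohol use is said to escalate through this age, so follow-up SD may exceed baseline SD. Several measures use a six-month recall window, so the 1-month and baseline windows overlap and ρ there may be high. Either would shrink the gain. This stands, and is why a range is given.

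**A reader might infer that about 40 dyads (320 − 280) drop out of the 1-month contrast**, because a standard repeated-measures MANCOVA uses complete rows. The documents do not support this as a finding. Aim 1 commits to intent-to-treat with everyone randomized. The Missing Data section names full information maximum likelihood, multiple imputation or modelling of missing-data bias. The Attrition analyses section describes analyzing all cases after imputation. Nowhere is listwise deletion proposed.

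**Conclusion.** The point holds as a matter of efficiency. The specified contrast is valid and unbiased, but it is less precise than an analysis that conditions on a baseline already in hand, except where kρ = 1.

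The 15% to 30% variance reduction should not be read as an established loss. It rests on ρ between 0.4 and 0.7, equal SDs and a single follow-up, none of which the documents give. For the same correlations and SD ratios of 0.8 to 1.2, the range is about 3% to 46%. The formulas are for a linear model.

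Nor do the documents support reading this as an underpowered trial. At the planned 5% of variance with 280 completers, a single test at alpha 0.05 keeps power of about 0.94 or more for ρ of 0.4 to 0.7 with equal SDs, even with the change contrast. The gain becomes material if the true effect is smaller, which is plausible against an active control, or after the multiplicity correction.

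**What to change.** In the Aim 1 paragraph, replace the 2 × 3 MANCOVA with a likelihood-based repeated-measures model for each outcome. The responses are the 1- and 6-month values. The terms are arm, visit, arm × visit, the baseline value of that outcome, and baseline × visit. A closely equivalent form keeps all three waves as responses and constrains baseline means to be equal across arms. State that all available follow-up data are used, in line with the existing intent-to-treat and missing-data commitments.

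If the latent growth model is also used for efficacy, state that group has no path to the latent intercept.

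The cost is SAP wording only. The baseline measures are already scheduled, no further participants are needed, and Mplus, which the plan already names, can fit these models.
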